The sequences were specifically chosen to: a) screen brain with the greatest specificity (FLAIR\*); b) allow for later volumetric analysis of the brain; and c) use the most sensitive technique for cortical and subcortical brain lesions (3D-DIR).

**B. Description of Population to be Enrolled:** The population will be a total of 300 women and men, of all races and ethnicities, between the ages of 18-30, inclusive, who have no symptoms of MS, but have at least one FDR with documented MS fulfilling McDonald 2017 criteria. Up to 1000 will be screened for inclusion, but some will be excluded due to inability to undergo a brain/spine MRI or have blood drawn, lack of interest after discussion of study requirements, or symptoms concerning for MS (the latter will be referred to a qualified neurologist for evaluation). FDRs with one or more siblings/parents with MS will be included, and more than one FDR of a proband MS patient will be allowed. A control group (based on # of FDRs with positive MRIs - we anticipate 15-30) of age- and sex-matched controls who have no known family members with MS (out to first cousins and grandparents) will have blood drawn and fill out the environmental questionnaire, but will not undergo a brain MRI. The controls will be matched 1:1:1 for those FDRs with positive MRI scans suggesting pre-symptomatic MS and those age-and sex-matched FDRs who do NOT have positive MRI scans suggesting pre-symptomatic MS. The ages were specifically chosen so as to have a good opportunity to collect an adequate number of MRI-positive, asymptomatic participants prior to the known median age of MS clinical onset (30 years), but not so young as to lower the likelihood of detecting asymptomatic brain MRI lesions.

1. FDR Inclusion Criteria
  - a. Male and female
  - b. All races and ethnicities
  - c. Ages 18-30
  - d. Must have a parent, sibling or child with MS fulfilling McDonald 2017 criteria
  - e. No symptoms suggestive of MS on formal screen
  - f. Ability to undergo a non-contrast MRI and venipuncture, and perform an environmental screen, mood screen and cognitive test
2. FDR Exclusion Criteria
  - a. Symptoms suggestive of MS on formal screen
  - b. Prior diagnosis of autoimmune disease that may be associated with CNS dysfunction and MRI lesions, e.g. Sjogren's
3. Non-FDR Inclusion Criteria
  - a. Male and female
  - b. All races and ethnicities
  - c. Ages 18-30

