  - d. Must NOT have a FDR (parent, sibling, child) or second degree relative (grandparent, aunt or uncle) with MS fulfilling McDonald 2017 criteria
  - e. No symptoms suggestive of MS on formal screen
  - f. Ability to undergo venipuncture and perform an environmental screen.
4. Non-FDR Exclusion Criteria
  - a. Symptoms suggestive of MS on formal screen
  - b. Prior diagnosis of autoimmune disease that may be associated with CNS dysfunction and MRI lesions, e.g. Sjogren's

FDR participants will be enrolled from among the FDRs of MS patients seen at the Rocky Mountain Multiple Sclerosis Center at the University of Colorado in Aurora, Colorado (RRMSC at CU). Our center has approximately 3500 unique patients, of whom nearly all have asymptomatic FDRs, many in the appropriate age range. Documented MS proband patients will be made aware of the study via interactions in the office, our newsletter, and IRB-approved information given to them for their FDRs. FDRs who are then interested will initiate contact with the research group. If this does not provide adequate enrollment, we will recruit by local advertisement through known offices of neurologists in the Denver and surrounding regions. Age- and sex-matched non-FDR controls will be recruited from the friends of FDRs who are positive on the screening MRI, or will be recruited from local recruitment in the department of Neurology offices, from those non-MS conditions. FDRs and controls will be screened on the phone for basic demographic criteria (e.g. age, location where they live) and a checklist of basic MS symptoms, and to be certain they do not have previously undiagnosed MS or other autoimmune/neoplastic disorders. Those with concerns for MS at screening will be referred to a qualified neurologist for assessment.

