### **C. Study Design and Research Methods:**

1. Prescreen FDRs by phone for ability to participate and lack of MS symptoms, using a standardized script to exclude those with overt MS symptoms. Proband MS patients will have documented MS by McDonald 2017 criteria.
2. Qualified FDRs will be scheduled for a study visit after completing a pre-screening questionnaire by phone. If they are not excluded by pre-screen, and wish to participate, a study visit will be scheduled. A waiver of documentation of consent will be obtained over the phone so as to instruct participants to fast from midnight prior to the first study visit. This will also allow them to fill out the environmental questionnaire on-line before their visit and at their convenience. The environmental survey must be completed at least three days prior to their visit. If not, the study visit will be canceled and rescheduled once its complete.
3. A study visit will include (See Table of activities below):
  - a. Read, ask questions regarding, and sign the consent.
  - b. Document completion of environmental questionnaire.
  - c. Obtain a measured height and weight, and compute a Body Mass Index (BMI)
  - d. Perform a non-contrast brain MRI (per section V.A)

- e. Perform a fasting Blood draw consisting of no more than 100 ccs of blood.
  - i. Blood drawn at the primary study visit will be a maximum of 100 ccs to be processed in the following fashion. Participants will not be made aware of their blood sample results
    - 1. 30 ccs for immediate cell sort by [name] into T and B lymphocytes, for CD40 expression studies, requiring primary analysis with fresh cells, and done on all samples. Also for HLA analysis.
    - 2. 20 ccs processed for delayed analysis of SNPs, viral serologies (Herpes Simplex Virus 1 and 2, Cytomegalovirus, Varicella-Zoster Virus, and Epstein-Barr Virus), vitamin D levels, and neuroaxonal (NfL - Quanterix) and myelin damage (lipids), which all can be performed on stored samples.
    - 3. 50 ccs processed and stored for delayed analysis of plasma and PBMCs, RNA and DNA, for studies not yet determined
- f. Perform the Perceived Stress Scale and the Neuro-QoL screen for anxiety and depression;
  - i. Participants screening for concerns for suicidality on the mood screen will be referred to an emergency room for evaluation.
- g. Perform a Symbol Digit Modality Test, a screen for cognitive function. The latter will be done in the written format.

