## **F. Data Analysis Plan: Statistical Approach**

- a. Based on previous studies, we estimate that 5-10% of the 300 FDRs (15-30) in our pilot study will exhibit an MRI endpoint. In order to test for associations with this endpoint to obtain valuable preliminary data, we will perform a nested case control study. We will match two controls per case based on age and sex: one group will be FDRs not fulfilling DIS on brain MRI; the second will be non-FDRs who are age- and sex-matched to FDRs who do, and do not, fulfill DIS on MRI scans. The non-FDRs will perform the environmental screen and undergo venipuncture for blood analysis identical to the other two groups, but will not have a MRI scan.
- b. Aim 1. Descriptive statistics

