- c. Aim 2. Association analyses; with individual factors and in a multiple risk factor analysis. In previous studies, HLA type, Vitamin D levels, Epstein Barr Virus exposure, smoking and early adult obesity have conferred a maximum odds ratio of 2-3 (many SNPs confer an odds ratio of 1.1-1.4) of developing MS when studied individually. In the GEMS study, participants were stratified into high and low risk categories based on a deep phenotyping of 64 SNPs, and environmental screen (including sex). Comparative analyses were performed on the high and low risk groups for both neurological exam and MRI measures. In this study, we plan to use the known risk factors, and add potential biomarkers (e.g. NfL, lipid levels) to define the risk of DIS in this population. For the power analysis we made the assumption that no single marker would exhibit an odds ratio greater than 2 for increased risk of DIS, and that all markers are additive. In this early proof of concept phase, with an estimated case sample size of 30 with 60 age- and sex-matched controls, our priori power analysis suggests an expected power ranging from 20-33% for risk factors such as smoking, obesity, and vitamin D deficiency. Using frequency and odds ratio from the GEMS study (OR = 2.9) we expect a power of 64% to detect an effect of HLA type risk. While this study will be statistically underpowered, and estimates will be imprecise, we expect that some results will have clinical significance. We plan to use these results and stored samples as the groundwork for larger, longitudinal, multi-site studies. These future studies will allow us to enroll samples sizes of greater than 500, necessary to reach 80-90% power. In reality, it is possible the effect some factors may depend on the levels of other factors. Example hypothesis that we will test: FDRs with DIS lesions are more likely to have been exposed to EBV as indicated by elevated EBV serology than FDRs of the same age and sex without DIS lesions. By extension, we will then define a risk score combining factors that are discriminatory, e.g. Vitamin D level, smoking, obesity, elevated NfL levels, impaired B cell anergy, and HLA type may each have a roughly 2 fold increased risk, whereas those with four of these factors have a six-fold increased risk of DIS on MRI.
- d. Aims 3 and 4 do not have statistical implications.

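### Controls are matched on age and sex only in a study open to all races and ethnicities, so ancestry imbalance could confound the HLA, SNP and vitamin D comparisons, by an amount the documents do not let us fix

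*Combined protocol and SAP*

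**What the plan says.** Section V.F.a sets the rule for the nested case-control study: "We will match two controls per case based on age and sex". One control per case is a first-degree relative (FDR) without DIS and the other is a non-FDR. Sections V, V.B and V.C.5 also name only age and sex.

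Section V.B describes the FDR cohort: "The population will be a total of 300 women and men, of all races and ethnicities, between the ages of 18-30, inclusive". The non-FDR inclusion list also admits "all races and ethnicities".

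The two control groups come from different places. DIS-negative FDRs are chosen from those already in the study. Under V.B, non-FDRs "will be recruited from the friends of FDRs who are positive on the screening MRI". The same section opens a second route, through neurology clinics, among people who attend for something other than MS. V.C.5 mentions only the friends.

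V.C.3.e provides for HLA typing and for "20 ccs processed for delayed analysis of SNPs, viral serologies", with vitamin D, NfL and lipids on the same sample. V.F.c tests markers singly and jointly and then combines the discriminatory ones into a risk score. It names no covariates. Neither there nor elsewhere is there an ancestry match, adjustment, stratification, restriction or genetic component.

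**The concern.** A marker whose frequency varies with ancestry will be associated with case status whenever ancestry is unevenly spread between cases and controls, even if it has no bearing on DIS. Matching on age and sex does nothing about this.

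The two contrasts are not equally exposed:

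- **Cases v DIS-negative FDRs.** Both groups come through the same recruitment. Systematic bias needs DIS frequency itself to differ by ancestry; chance imbalance is also possible.
- **Cases v non-FDRs.** FDRs come chiefly from families of one MS centre's patients. Non-FDRs come from friends or from neurology offices, with no ancestry condition, so the mix can differ through recruitment alone.

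What is at stake is which markers enter the risk score, and whether the control set and stored samples suit the larger studies that V.E and V.F.c describe.

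**Working it through.** **The plan's own figures.** V.F.c gives 20-33% power for common factors and 64% for HLA at an odds ratio (OR) of 2.9, with 30 cases and 60 controls. Neither alpha nor control exposure frequencies are stated. I assume two-sided 5% and take the exposure in cases as p1 = OR·p0/(1 − p0 + OR·p0).

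- OR 2: power is 20.1% at p0 = 9% and 32.9% at p0 = 30%.
- OR 2.9: power is 64.2% at p0 = 28% and 64.0% at p0 = 42%. With 30 controls instead of 60 it peaks near 52%.

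The stated figures are attainable. On these assumptions the 64% uses all 60 controls, and under 1:1:1 matching 30 of them are non-FDRs.

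**Model for the bias.** Take two ancestry groups, A and B, and a marker with no effect on DIS within either. If s is the share of A in a study group, carriage in that group is s·fA + (1 − s)·fB. The spurious OR compares the odds of carriage in cases and controls. The documents give no ancestry mix and no marker or DIS frequency by ancestry, so every input below is an assumption. Carriage is fA = 25-30% and fB = 10%.

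**(a) Cases v DIS-negative FDRs.** B is 10-30% of FDRs; DIS is 8-9% in A and 3-4% in B.

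- Low end (B 10%, DIS 8% v 4%, carriage 25% v 10%): A's share of cases is 0.9×0.08/(0.9×0.08 + 0.1×0.04) = 94.7%. Its share of DIS-negatives is 0.9×0.92/(0.9×0.92 + 0.1×0.96) = 89.6%. Carriage is 24.2% v 23.4%, **OR 1.04**.
- High end (B 30%, DIS 9% v 3%, carriage 30% v 10%): A's shares are 87.5% and 68.6%. Carriage is 27.5% v 23.7%, **OR 1.22**.

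Overall DIS is 7.6% and 7.2% in these two settings, within the 5-10% the plan expects. If DIS frequency is the same in both groups, the systematic OR is 1.00.

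**(b) Cases v non-FDRs.** B is 10-15% of cases and 20-40% of non-FDRs.

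- Low end (15% v 20%, carriage 25% v 10%): 22.75% v 22.0%; (0.2275/0.7725)/(0.22/0.78) = **1.04**.
- High end (10% v 40%, carriage 30% v 10%): 28% v 22%; (0.28/0.72)/(0.22/0.78) = **1.38**.

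**Sensitivity.** With a narrow gap in carriage (25% v 20%), A at 90% of cases and 85-60% of controls, the OR is only 1.01-1.09. For vitamin D deficiency, assumed at 20% v 40-60%, A at 90% of cases and 80-60% of controls gives 0.89 to 0.56, or 1.1 to 1.8 if the imbalance runs the other way. The far end needs both a 40-point gap in deficiency and a 30-point imbalance. Matching or stratifying on ancestry returns the OR to 1.00 in this model.

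**Against sampling error.** For the high end of (b) with 30 v 30:

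- SE under the null = √(0.25×0.75×2/30) = 0.112, so the rejection limit is 1.96×0.112 = 0.219.
- SE at the assumed frequencies = √((0.28×0.72 + 0.22×0.78)/30) = 0.112.
- Rejection probability = Φ((0.06 − 0.219)/0.112) + Φ((−0.06 − 0.219)/0.112), about 8% instead of 5%.

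The high end of (a) gives about 6%. The 95% interval for such an OR spans roughly a factor of 3 either way.

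**At larger size.** V.F.c foresees more than 500 people. Take 167 cases v 334 controls (assumed split), all controls carrying the imbalance, carriage 25% v 10% and B 10% of cases. With B at 20% of controls (OR 1.09), rejection is 6.8%. With B at 40% (OR 1.31), it is 22.3%.

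**The case against.** The strongest reply is that nothing in the documents shows an imbalance. They give no ancestry mix and do not say that these markers or DIS vary by ancestry. The upper values need a threefold difference in DIS frequency or a 30-point difference in ancestry share. Aim 2 is about DIS among FDRs, which is the less exposed contrast, and friends of MRI-positive FDRs may share their background. The plan already calls itself underpowered and imprecise. Its silence on covariates is general and does not rule out later adjustment.

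Most of that stands, and it limits the point to a possible bias of unknown size. Three parts do not dispose of it. Friendship is not an ancestry match, and the neurology-office route lacks even that. Conceding imprecision does not concede confounding: the first shrinks as numbers grow and the second does not. Adjustment later cannot recover a poorly matched set of non-FDR controls.

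A reader might infer more than the documents support:

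- **That the bias is as large as the effects sought.** It overlaps the range in "many SNPs confer an odds ratio of 1.1-1.4", but that remark concerns earlier studies of MS. The power analysis here uses ORs up to 2, and 2.9 for HLA, and the example risk score lists no individual SNP. The range above also rests on HLA-type carriage gaps, not on SNP frequencies.
- **That an HLA finding could be wholly an ancestry artefact.** The largest HLA-type value above is 1.38, far from 2.9.

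**Conclusion.** The gap is real: the control groups are formed without regard to ancestry, and no analysis makes up for it. The bias could be about 1.04-1.22 within FDRs and 1.04-1.38 against non-FDRs for an HLA-type marker. Both ranges rest on assumed carriage, ancestry shares and DIS frequencies. It would be negligible if the enrolled groups are nearly all of one ancestry. In a pilot of 15-30 cases it is minor beside sampling error. The main harm would be to the risk score and control set carried into later studies. This is a cheap improvement best made before controls are selected; it does not invalidate the design.

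**What to change.** - Record self-reported race/ethnicity for every participant. The documents do not show whether the screening call or questionnaire already does so.
- In V.B, V.C.5 and V.F.a, add it to age and sex when choosing the DIS-negative FDR control. With 300 FDRs and 15-30 cases there are 270-285 to choose from.
- Match the non-FDR control on it where feasible.
- In V.F.c, where no such match is found, and for HLA and SNP analyses generally, adjust with a single sparse ancestry term (for example, largest group v other), since 15-30 cases will not support more.

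Genotype-based components and a sensitivity analysis restricted to the largest ancestry group are optional, because restriction would reduce an already small case group.

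The cost is one more field and one model term, with slightly looser age matching or slower non-FDR recruitment for a few cases. No extra visit or blood is needed.

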Innovation – The GEMS study described above is one approach to identification of early MS, but it had several limitations. It used a pre-defined risk score, including a SNP analysis of just 64 SNPs, when more recent analysis suggests over 200 may be relevant. It employed a long, detailed, and expensive brain MRI, but did not include spine or FLAIR\* analysis. The cost limited participation. GEMS did not include potential immunological markers, markers of CNS damage (such as NFL or lipids), activity levels, or a detailed environmental screen. Due to privacy issues, they were unable to verify the MS diagnosis in FDRs. Finally, it was limited to 100 patients, of which only 65 (females only) were analyzed. Other studies (as yet unpublished) designed to look at risk factor algorithms for development of MS are employing larger numbers of patients, but minimal, if any, MRI analyses, no or minimal immunological or CNS damage markers, and no activity levels. Most importantly, they are using full clinical diagnosis of MS as the outcome measure, greatly limiting the number of “positive” patients, and biasing toward a much later time in the disease process. Thus, our study has great innovative value for several reasons:

- a. We will define pre-symptomatic MS in 300 FDRs using stringent MRI criteria, including FLAIR\* sequences, thus significantly increasing sensitivity and detection in the prodromal phase. Proband MS patients will be defined from our own population of MS patients known to fulfill formal diagnostic criteria for MS.
- b. We will analyze genetic, immunological, vitamin, lipid, viral, and CNS damage markers; activity levels; and a mood and cognitive screen, with the goal of defining an expanded risk stratification scheme, not a pre-defined one
- c. We will include a detailed environmental screen, employing approaches very similar to the DAISY study, and [name], lead epidemiologist in DAISY, will participate as a Co-PI.
- d. We will compare those FDRs with and without brain MRI abnormalities to each other, and to non-FDR controls (blood and environmental screen, not MRI)
- e. We will create a biobank of blood, both plasma and PBMCs, including pre-processed serum/plasma and RNA, allowing us to add to the risk stratification model over time.

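### Aim 2 does not state which control contrast makes a factor discriminatory for DIS, and its power counts unscanned non-FDRs as DIS controls, so family status can pass for an association with DIS

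*Combined protocol and SAP*

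**What the plan says.** - **Target.** Section II places Aim 2 under a heading limited to asymptomatic FDRs. The score is for DIS, and section V.F.c repeats that the risk concerns this population.
- **Control groups.** Section V.F.a introduces a nested case-control study to test for associations with the MRI endpoint, with two matched controls for each case: "one group will be FDRs not fulfilling DIS on brain MRI; the second will be non-FDRs who are age- and sex-matched to FDRs". The non-FDRs give blood and complete the environmental screen "but will not have a MRI scan".
- **Matching.** Section V.B: "The controls will be matched 1:1:1 for those FDRs with positive MRI scans suggesting pre-symptomatic MS". Each case therefore has one DIS-negative FDR and one non-FDR.
- **Comparisons.** Section III (Innovation, item d): "We will compare those FDRs with and without brain MRI abnormalities to each other, and to non-FDR controls". Neither comparison is called primary.
- **Power.** Section V.F.c works "with an estimated case sample size of 30 with 60 age- and sex-matched controls". It gives 64% for HLA at an odds ratio of 2.9, and 20-33% for markers such as smoking, obesity and vitamin D deficiency, with no single marker assumed to exceed an odds ratio of 2.
- **Hypothesis.** The only one written out, labelled an example, compares EBV serology in FDRs with and without DIS lesions.
- **Score.** The next sentence reads: "By extension, we will then define a risk score combining factors that are discriminatory". HLA type is among the examples. No comparator, test or threshold is given.
- **Number of cases.** Section V.F.a: "we estimate that 5-10% of the 300 FDRs (15-30) in our pilot study will exhibit an MRI endpoint".

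**The concern.** The two contrasts answer different questions. DIS-positive v DIS-negative FDR asks what separates relatives with lesions from relatives without them, which is what Aim 2 sets out to find. DIS-positive FDR v non-FDR compares people who differ in family status by design and, in addition, in DIS. Family status cannot be adjusted away, because it coincides completely with case status in that contrast. The DIS status of the non-FDRs is also unknown.

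Factors that run in families with MS (HLA, other genes, household exposures) will differ between FDRs and non-FDRs even if they have nothing to do with DIS. If such a factor is called discriminatory on the strength of the non-FDR or pooled comparison, it enters the DIS score but does not separate DIS-positive from DIS-negative FDRs. The results are meant as groundwork for larger studies, so the wrong markers could be carried forward.

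**Working it through.** **1. Who the 60 controls are.** 30 cases at 1:1:1 give 30 DIS-negative FDRs + 30 non-FDRs = 60.

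**2. Reproducing the stated power.** Inputs from section V.F.c: 30 cases, 60 controls, odds ratio 2.9. The documents give neither the significance level nor the exposure frequency; I assume two-sided 5% and vary the control exposure p0.

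Formulas: p1 = OR·p0 / (1 − p0 + OR·p0); power = Φ[(|p1 − p0| − 1.96·se0)/se1], with se0 from the pooled proportion and se1 from the separate proportions.

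At p0 = 0.30: p1 = 0.87/1.57 = 0.554, a difference of 0.254.
- 30 v 60: pooled proportion 0.385, se0 = 0.1088, se1 = 0.1083. (0.2541 − 0.2132)/0.1083 = 0.38, power 65%.
- 30 v 30: pooled proportion 0.427, se0 = 0.1277, se1 = 0.1234. (0.2541 − 0.2503)/0.1234 = 0.03, power 51%.

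| Setting | 30 v 60 | Stated | 30 v 30 |
|---|---|---|---|
| OR 2.9, p0 0.25-0.45 | 63-65% | 64% | 49-52% |
| OR 2, p0 0.10-0.40 | 21-34% | 20-33% | 15-26% |

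Over all p0, two-sided 30 v 30 never exceeds 52% (OR 2.9) or 26% (OR 2). The stated figures therefore fit the full 60, half of them unscanned non-FDRs. A one-sided 5% test with 30 v 30 would also give 62-65% for HLA at p0 0.25-0.45, so the arithmetic alone is not proof; but the plan itself states 60 controls.

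**3. How far a familial factor with no link to DIS is shifted.** Assumptions, none given in the documents: a dominant allele carried by 15-30% of non-FDRs; an odds ratio for MS in probands of 2 to 2.9; Mendelian sharing; DIS independent of the allele within FDRs.

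Example with 20% carriage and proband odds ratio 2.9:
- Allele frequency q = 1 − √0.80 = 0.106.
- Proband genotypes (0, 1, 2 copies), weighted 1 : 2.9 : 2.9, are 0.580, 0.397, 0.023.
- A parent or child of the proband is a non-carrier with probability 0.580 × 0.894 + 0.397 × 0.447 = 0.696, so FDR carriage is 0.304 (siblings: 0.307).
- FDR v non-FDR odds ratio: (0.304/0.696)/(0.20/0.80) = 1.75.
- Pooled controls: exposure (0.304 + 0.20)/2 = 0.252, giving an odds ratio of (0.304/0.696)/(0.252/0.748) = 1.30. On the log scale, ln 1.30/ln 1.75 = 0.47, about half the bias.
- Within FDRs the odds ratio is 1.

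Over 15-30% carriage, the spurious odds ratio against non-FDRs is about 1.7-1.8 for proband odds ratio 2.9 and about 1.4 for 2.

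**4. False-positive rates.** Two-proportion z-test, two-sided 5%, equal group sizes (pooled: twice as many controls as cases), over the whole range of assumptions in step 3:

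| Cases | v non-FDR | v pooled | v DIS-negative FDR |
|---|---|---|---|
| 30 | 8-16% | 7-9% | about 5% |
| 15 | 6-11% | 6-7% | about 5% |

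The upper ends belong to proband odds ratio 2.9, the lower ends to 2.

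**The case against.** Several lines point to the within-FDR contrast: the heading over Aim 2, the reference to risk in this population, and the EBV example, from which the score follows as an extension. A reader might infer that the plan is wholly silent on the comparator. It is not, and that reading should not be made.

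A reader might also infer that the plan directs the analyst to qualify factors against non-FDRs, or to pool the controls in analysis. No sentence says so; sections III, V and V.C describe separate comparisons, and pooling appears only through the 60 in the power statement.

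Two cautions on size also stand. The odds ratio of 2.9 is taken from the GEMS study for the power calculation and is not described as an odds ratio for MS in probands; using it that way is my assumption. And if the two contrasts often disagreed on a marker, a reader might take that as evidence of confounding. At this sample size, disagreement is expected even between two unbiased control groups, and the plan openly admits low power.

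Finally, this is a declared proof of concept. That excuses imprecision, but not bias towards family markers. An example for one marker is not an entry rule, and the power statement in the same paragraph uses the other control group as well.

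**Conclusion.** The point holds in a limited form. The plan leans towards the within-FDR contrast but never makes it the rule for entry to the score. It also names non-FDRs as a control group for associations with DIS and counts them in its power. An analyst could use either contrast, or the pooled set, and still comply.

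The consequence is moderate. The pooled route, the one suggested by the power statement, raises the false-positive rate for an HLA-type factor only slightly, and the non-FDR contrast at most about threefold. These sizes rest on the assumed carriage, proband odds ratios and Mendelian model, and shrink towards 15 cases. The direction does not depend on them: any factor that is commoner in FDRs than in non-FDRs is biased towards an apparent link with DIS. The plan should be amended before the Aim 2 analysis.

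**What to change.** In section V.F, items a and c:

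1. Name DIS-positive FDR v DIS-negative FDR as the only contrast that can qualify or weight a factor for the DIS score.
2. Keep DIS-positive FDR v non-FDR and DIS-negative FDR v non-FDR as separate, descriptive comparisons. The second shows the difference associated with FDR status and helps in reading the first.
3. State that the two control groups are not pooled for any association with DIS.
4. Restate power for 30 v 30, using the last column of the power table above, with the significance level and exposure frequencies given. With 15 v 15 it is at most 29% for odds ratio 2.9 and 15% for odds ratio 2.

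The cost is a few sentences and no new data. The downside is fewer controls per test and a less favourable stated power. For markers measured in all FDRs at Visit 1, the sponsor could consider using every DIS-negative FDR as a control: with 30 v 270 (300 − 30), power for odds ratio 2.9 is about 78-79% at control exposure 0.25-0.40. That is not possible for B cell anergy, which is measured only in the matched subset.
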